### 3.4 Discontinuation Criteria for Individual Subjects

A discontinuation means that a subject who has enrolled in the study prematurely terminates study treatment prior to the completion of all protocol-required elements.

The subject is free to withdraw from the study treatment and/or study for any reason and at any time without giving reason for doing so and without penalty or prejudice. The investigator is also free to terminate a subject's involvement in the study at any time if this is considered necessary because of the subject's clinical condition.

Discontinuation Criteria for Individual Subjects:

The investigator/sub-investigator should discontinue the study if any of the following criteria are met:

1. Subject withdraws consent.
2. The study drug is not sufficiently effective, and a change in treatment method is deemed to be in the subject's best interest by the investigator or sub-investigator.
3. Symptomatic CPK elevation, defined as  $CPK > 1.5 \times ULN$  with severe unusual myalgia, muscular weakness, or muscle twitching\*.  
\* Muscle twitching: A condition in which there is a cramp in a muscle, such as cramps in the calves
4. Any event of myopathy defined as severe unusual myalgia, muscular weakness, and muscle twitching\* regardless of CPK level that persists for at least 2 weeks or that worsens rapidly within 2 weeks.  
\* Muscle twitching: A condition in which there is a cramp in a muscle, such as cramps in the calves
5. Subject infected with HBV who has tested positive for either of or both of HBc and HBs antibodies and is found to be positive for HBV-DNA assay during the study period. Abrupt discontinuance of immunosuppressive therapy may precipitate severe or fulminant hepatitis. Therefore, when HBV reactivates, nucleic acid analog therapy should be immediately initiated, and a hepatologist should be consulted regarding the continuation of ASP015K and concomitant DMARD (unique to Japan: as indicated by "Proposal for Management of Rheumatic Disease Patients with Hepatitis B Virus Infection Receiving Immunosuppressive Therapy" by the Japan College of Rheumatology).

- CONFIDENTIAL -

6. Subject has a malignant tumor.
7. Subject has an adverse event (AE) such as a serious infection, and the investigator or sub-investigator considers that it is not in the subject's best interest to continue the study.
8. Subject receives or requires a prohibited concomitant medication (including other study drugs) or prohibited concomitant therapy that may affect the evaluation of efficacy; subject receives or requires live vaccine or live attenuated vaccine.
9. Subject receives or requires drug interruption for a longer period than that stipulated for interruption.
10. Subject is deemed lost to follow-up by the investigator/sub-investigator (subject can no longer come to the study center; subject can no longer be contacted, etc.).
11. It comes to light after the administration of the first dose of study drug that the inclusion criteria were not met at the time of case enrollment or that criteria for exclusion were met. It comes to light that there was some other major deviation from the protocol.
12. Investigator or sub-investigator decides it is in the subject's best interest to discontinue.
13. The sponsor has requested that administration of the study drug be discontinued because of a safety problem in a particular subject, or the sponsor has decided to discontinue the study altogether.
14. Subject has QTc < 300 msec on ECG measurements and has QTc < 300 msec at retest.

Subjects who discontinue early from the study should be given the necessary tests and assessments specified to be performed at end of treatment/early termination within 2 days after taking the final dose of the study drug if possible (see "Table 1, Schedule of Assessments"). Moreover, these subjects should receive the tests and assessments scheduled for end of study (at time of follow-up). These assessments and tests will be conducted only if the investigator/ sub-investigator decides necessary.

If the discontinuation has been for reasons of AEs, appropriate treatment should be provided as necessary.

Subjects with early termination will be treated as discontinuations, and the investigator/sub-investigator must clearly identify the date of discontinuation and the reason for discontinuation, as well as retain all clinical study data on the discontinuations and submit it to the sponsor in the CRF, report of follow-up investigation, etc.

The Appendix 6 entitled "Liver Safety Monitoring and Assessment" describes liver function tests raised that provide grounds for discontinuation. Refer to this if liver function tests raised is observed.

### **3.4.1 Suspension, Interruption, and Resumption of the Study Drug**

If either of the criteria in Section 3.4.1.1, Criteria for Suspension or Interruption of the Study Drug, is met during the treatment period with the study drug, the investigator or sub-investigator is to suspend or interrupt administration of the study drug without delay. Administration of the study drug may be resumed after the initiation of suspension or

- CONFIDENTIAL -

interruption if a retest shows that none of the following criteria are met, provided that the investigator or sub-investigator deems resumption to be in the subject's best interest, taking the risk/benefit ratio into consideration.

#### Suspension of the study drug

Administration of the study drug may be suspended within the scope of the below stipulations if the investigator or sub-investigator deems a temporary discontinuation (suspension) of dosing to be necessary. Suspension of the study drug beyond the scope of the following stipulation is handled as interruption:

- Suspension is defined as a temporary discontinuation of study drug administration for 7 days or less.
- If administration of the study drug is suspended repeatedly, the discontinuation of the clinical study for the particular subject should be considered in consultation with the sponsor.

#### Interruption of the study drug

Administration of the study drug may be interrupted within the scope of the below stipulations if the investigator or sub-investigator deems a temporary discontinuation (interruption) of dosing for a period exceeding 7 days to be necessary. If a subject requires interruption beyond the scope described below, the subject has to be withdrawn from the study.

- Interruption is defined as a temporary discontinuation of study drug administration for a period exceeding 7 days.
- Interruption may not exceed a maximum of 4 consecutive weeks.
- Up to 2 interruptions per year may be allowed. Moreover, they must be separated by an interval of 16 weeks or more.

#### 3.4.1.1 Criteria for Suspension or Interruption of the Study Drug

If either of the below criteria is met during the treatment period with the study drug, the investigator or sub-investigator is to suspend or interrupt the administration of the study drug without delay. The administration of the study drug may be resumed after the initiation of suspension or interruption if a retest shows that none of the following criteria are met:

1. Subject has any of the following laboratory values. Administration of the study drug is to be discontinued until a retest shows that none of the following criteria are met:
  - Hemoglobin < 8.0 g/dL
  - ANC < 500/ $\mu$ L
  - Absolute lymphocyte count < 500/ $\mu$ L
  - Platelet count < 50000/ $\mu$ L
  - Serum creatinine > 150% of baseline at 2 consecutive Scheduled Visits
  - CPK > 10  $\times$  ULN
2.  $\beta$ -D-glucan > ULN [in case of Japan:  $\geq$  11 pg/mL]

- CONFIDENTIAL -

3. Subject requires a concomitant medication that is prohibited because of a possible drug interaction.
4. Suspected pregnancy.
5. The investigator or sub-investigator considers suspension or interruption of the study drug to be in the subject's best interest.
6. The sponsor has requested suspension or interruption of the study drug because of a safety problem in a particular subject.

- CONFIDENTIAL -

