	
without delay. Administration of the study drug may be resumed after the initiation of suspension or interruption if a retest shows that none of the following criteria are met, provided that the investigator or sub-investigator deems resumption to be in the subject's best interest, taking the risk/benefit ratio into consideration:
 
 
1. Subject has any of the following laboratory values: 
 
• Hemoglobin < 8.0 g/dL
 
• ANC < 500/<math>\mu</math>L
 
• Absolute lymphocyte count < 500/<math>\mu</math>L
 
• Platelet count < 50000/<math>\mu</math>L
 
• Serum creatinine > 150% of baseline at 2 consecutive Scheduled Visits
 
• CPK > 10 <math>\times</math> ULN
 
 
 
2. <math>\beta</math>-D-glucan > ULN [in case of Japan: <math>\geq</math> 11 pg/mL]
 
3. Subject requires a concomitant medication that is prohibited because of a possible drug interaction.
 
4. Suspected pregnancy.
 
5. The investigator or sub-investigator considers suspension or interruption of the study drug to be in the subject's best interest.
 
6. The sponsor has requested suspension or interruption of the study drug because of a safety problem in a particular subject.
 
 
Suspension of the study drug Administration of the study drug may be suspended within the scope of the below stipulations if the investigator or sub-investigator deems a temporary discontinuation (suspension) of dosing to be necessary. Suspension of the study drug beyond the scope of the following stipulation is handled as interruption:
 
 
• Suspension is defined as a temporary discontinuation of study drug administration for 7 days or less.
 
• If administration of the study drug is suspended repeatedly, the discontinuation of the clinical study for the particular subject should be considered in consultation with the sponsor.
 
 
Interruption of the study drug Administration of the study drug may be interrupted within the scope of the below stipulations if the investigator or sub-investigator deems a temporary discontinuation (interruption) of dosing for a period exceeding 7 days to be necessary. If a subject requires interruption beyond the scope described below, the subject has to be withdrawn from the study.
 
 
• Interruption is defined as a temporary discontinuation of study drug administration for a period exceeding 7 days.
 
• Interruption may not exceed a maximum of 4 consecutive weeks.
 
• Up to 2 interruptions per year may be allowed. Moreover, they must be separated by an interval of 16 weeks or more.
 

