#### 5.4.4.1 CPK Monitoring

If a CPK elevation is observed after administration of the study drug begins, CPK will be monitored as follows.

- If CPK is  $> 3 \times \text{ULN}$  after the start of study drug administration and the subject is asymptomatic, retest CPK to confirm the CPK value, preferably within approximately 1 week from the previous blood sampling. In addition, retest CPK weekly, starting from the date of the initial CPK elevation to  $> 3 \times \text{ULN}$ , until CPK is  $\leq 3 \times \text{ULN}$  or until the investigator or sub-investigator considers CPK to have achieved a steady state. If the retest cannot be performed within 1 week from the collection time of the blood sample with the CPK value because of which the monitoring was initiated, suspension or interruption of the study drug should be considered until results of the retest are known.
- If CPK is  $> 3 \times \text{ULN}$  already at baseline and is elevated to  $> 2 \times \text{baseline}$  after the start of study drug administration and the subject is asymptomatic, retest CPK to confirm the value, preferably within approximately 1 week from the previous blood sampling. In addition, retest CPK weekly, starting from the date of the initial CPK elevation to  $> 2 \times \text{baseline}$  value, until CPK is  $\leq 2 \times \text{baseline}$  or until the investigator or sub-investigator considers CPK to have achieved a steady state. If the retest cannot be performed within 1 week from the collection time of the blood sample with the CPK value because of which the monitoring was initiated, suspension or interruption of the study drug should be considered until the results of the retest are known.
- If CPK  $> 10 \times \text{ULN}$  is confirmed after the start of study drug administration, suspend or interrupt the administration of the study drug immediately and retest CPK (see Section 3.4.1, Suspension, Interruption, and Resumption of the Study Drug).
- If a symptomatic CPK elevation (CPK elevation  $> 1.5 \times \text{ULN}$ , accompanied by unusual severe myalgia, muscular weakness, and muscle twitching) is reported by the investigator or sub-investigator, the study will be discontinued (see Section 3.4, Discontinuation Criteria for Individual Subjects).

At the time of CPK monitoring, the following parameters will also be measured. The answers given in the subject questionnaire will be recorded in the eCRF.

- Laboratory tests  

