#### 5.4.4.2 Liver Safety Monitoring and Assessment

If laboratory testing for a subject enrolled in a study and receiving the study drug reveals  $> 3 \times \text{ULN}$  elevation in serum aminotransferases (ALT, AST) or TBL elevation to  $> 2 \times \text{ULN}$ , the liver function test must be repeated including at least the 4 parameters ALT, AST, ALP,

- CONFIDENTIAL -

and TBL. The retest is to be performed between 48 hours and 72 hours after notification of the test results.

See Appendix 6 “Liver Safety Monitoring and Assessment” for the assessment of additional information and liver function values in the monitoring.

If a subject enrolled in a study and receiving the study drug reveals  $> 3 \times$  ULN elevation in serum aminotransferases (ALT, AST) concurrently with bilirubin  $> 2 \times$  ULN, the investigator will decide whether the event is SAE. Even if the abnormal change is not considered by the investigator or sub-investigator to be SAE, it has to be reported to the sponsor or CRO as in the case of SAE.

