## **5.8 Total Amount of Blood**

The total amount of blood drawn for samples will differ from subject to subject in this study because duration of participation in the study will differ depending upon the subject.

The volume of blood drawn per sample and the total annual sample volume are shown in the table below. In addition, blood samples are collected for ESR determination performed at each study center; the volume will differ from center to center (approximately 1 to 2 mL per sample). See Table 1, Schedule of Assessments, for details regarding the blood-sampling schedule.

Blood samples will be taken at other times as necessary to follow up on laboratory test values obtained.

- CONFIDENTIAL -

[Subjects who transferred from RAJ1]

Assessment	Volume of sample	Total annual sample volume (No. of draws)	
		First year	2nd year and later
Hematology	2 mL	28 mL (14 times)	8 mL (4 times)
Biochemistry (including CRP and lipid profile tests)	14 mL	196 mL (14 times)	56 mL (4 times)
Lymphocyte subsets	2 mL	4 mL (2 times)	2 mL (1 time)
Total	18 mL	228 mL	66 mL

[Subjects who transferred from RAJ3 or RAJ4]

Assessment	Volume of sample	Total annual sample volume (No. of draws)	
		First year	2nd year and later
Hematology	Japan: 2 mL Korea: 3 mL Taiwan: 3 mL	Japan: 10 mL (5 times) Korea: 15 mL (5 times) Taiwan: 15 mL (5 times)	Japan: 8 mL (4 times) Korea: 12 mL (4 times) Taiwan: 12 mL (4 times)
Biochemistry (including CRP and lipid profile tests)	Japan: 14 mL Korea: 15.5 mL Taiwan: 13.5 mL	Japan: 70 mL (5 times) Korea: 77.5 mL (5 times) Taiwan: 67.5 mL (5 times)	Japan: 56 mL (4 times) Korea: 62 mL (4 times) Taiwan: 54 mL (4 times)
Lymphocyte subsets	Japan: 2 mL Korea: 3 mL Taiwan: 3 mL	Japan: 4 mL (2 times) Korea: 6 mL (2 times) Taiwan: 6 mL (2 times)	Japan: 2 mL (1 time) Korea: 3 mL (1 time) Taiwan: 3 mL (1 time)
Total	Japan: 18 mL Korea: 21.5 mL Taiwan: 19.5 mL	Japan: 84 mL Korea: 98.5 mL Taiwan: 88.5 mL	Japan: 66 mL Korea: 77 mL Taiwan: 69 mL

\* Additional 5 mL of blood per sample needs to be drawn in Japan and Taiwan, and 8.5 mL in Korea at the scheduled visits after initiation of study drug administration if HBV-DNA assay is performed.

\* Additional 4 mL of blood per sample needs to be drawn in Japan, and 5 mL in Korea and Taiwan if determination of CK-MB, troponin T, and aldolase is performed.

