## 7 STATISTICAL METHODOLOGY

A detailed elaboration of the statistical analysis will be included in a separate statistical analysis plan based on the opinions and advice from a medical expert. After review, it will be finalized prior to data lock. For the analyses of efficacy and pharmacodynamics variables in this extension study, values at the baseline in the previous studies (RAJ1, RAJ3, and RAJ4) will be used as the baseline values. However, changes from baseline values of this extension study will also be examined where appropriate. For the evaluation of safety, Week 0 of this extension study (015K-CL-RAJ2) will be referred to as the baseline; however, changes from baseline values of the previous studies (RAJ1, RAJ3, and RAJ4) will also be examined where appropriate.

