## (2) Laboratory Tests (Hematology, Biochemistry [including Fasting Lipid Profile Test], Urinalysis)

Time points defined in analysis	Reference date*	Acceptable time range
Week 0	Day 1	Day 1
Week 2	Day 15	Day 12 to Day 18
Week 4	Day 29	Day 22 to Day 36
Week 8	Day 57	Day 50 to Day 64
Week 12	Day 85	Day 78 to Day 92
Week 16	Day 113	Day 106 to Day 120
Week 20	Day 141	Day 134 to Day 148
Week 24	Day 169	Day 162 to Day 176
Week 28	Day 197	Day 190 to Day 204
Week 32	Day 225	Day 218 to Day 232
Week 36	Day 253	Day 246 to Day 260
Week 40	Day 281	Day 274 to Day 288
Week 44	Day 309	Day 302 to Day 316
Week 48	Day 337	Day 330 to Day 344
Week 60	Day 421	Day 407 to Day 435
Week 72	Day 505	Day 491 to Day 519
Week 84	Day 589	Day 575 to Day 603
Week 96	Day 673	Day 659 to Day 687
Week 108	Day 757	Day 743 to Day 771
Week 120	Day 841	Day 827 to Day 855
Week 132	Day 925	Day 911 to Day 939
Week 132 + 12 × x	$\text{Day } 7 \times (132 + 12 \times x) + 1$	$\text{Day } 7 \times (132 + 12 \times x) - 13$ to $\text{Day } 7 \times (132 + 12 \times x) + 15$
End/discontinuation of treatment	Day of the last dose	Day 2 to 2 days after the last dose
End of the study (at time of follow-up)	28 days after the last dose	21 to 35 days after the last dose

\*: Day 1 represents the first day of study treatment.

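### The only numeric creatinine stop needs two consecutive Scheduled Visits, so on 12-week visits it cannot act until about 84 days after a first high value, even one above 3.0 x baseline

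*Protocol*

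**What the plan says.** Protocol Section 3.4.1.1, item 1, lists six laboratory limits at which dosing must be suspended or interrupted without delay; item 2 adds beta-D-glucan. The creatinine limit is "Serum creatinine > 150% of baseline at 2 consecutive Scheduled Visits", and the Synopsis repeats it ("150% of baseline at 2 consecutive Scheduled Visits"). As written there, each of the other limits needs one value, and none refers to Scheduled Visits.

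Two other laboratory signals have timed retests. For raised CPK without symptoms, Section 5.4.4.1 tells the site to "retest CPK to confirm the CPK value, preferably within approximately 1 week from the previous blood sampling". For liver tests, Section 5.4.4.2 says: "The retest is to be performed between 48 hours and 72 hours after notification of the test results". No section sets a timed creatinine retest, and no creatinine or eGFR value appears in the discontinuation criteria of Section 3.4. Section 5.8 allows extra sampling in general terms: "Blood samples will be taken at other times as necessary to follow up on laboratory test values obtained".

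Creatinine is part of the biochemistry panel at each study visit. Under Table 1, note v, only RAJ1 subjects have visits between the 12-week visits, the last at Week 44. The SAP treats 3.0 x the Week 0 value as a separate level twice: as a reporting band in Section 7.5.2.3 and as a Grade 3 limit in Appendix 9.

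**The concern.** Asking for persistence at 150% of baseline is reasonable, since a single modest rise may be noise. The difficulty is that nothing replaces persistence when one value is already far higher. A subject at three or four times baseline, with a repeat a week later that agrees, still meets no numeric criterion until the next Scheduled Visit. Until then, suspension rests on judgement alone.

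Protocol Section 1.3 reports raised creatinine in RAJ1 (with lower eGFR), RAJ3 and RAJ4, so the parameter is relevant to this drug. At stake is up to one visit interval of continued daily dosing after a marked rise.

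**Working it through.** **The plan's own visit days.** Visit day = 7 x week + 1, with a window of ±7 days for Weeks 12-48 and ±14 days from Week 60. Week 60: 7 x 60 + 1 = 421, ±14 gives 407-435, matching "Day 407 to Day 435" in Protocol Section 7.8.3 (2). Week 72: 7 x 72 + 1 = 505, ±14 gives 491-519, matching "Day 491 to Day 519". The other 12-week rows from Week 12 to Week 132 reproduce in the same way.

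**Delay to the earliest numeric stop.** This assumes that the first high value is at a Scheduled Visit and the next Scheduled Visit is also above 150%.
- Minimum = start of next window minus end of current window.
- Maximum = end of next window minus start of current window.

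| Visit pair | Windows (days) | Minimum | Nominal | Maximum |
|---|---|---|---|---|
| Week 12 to 24 (same for 24-36, 36-48) | 78-92; 162-176 | 162 - 92 = 70 | 84 | 176 - 78 = 98 |
| Week 48 to 60 | 330-344; 407-435 | 407 - 344 = 63 | 84 | 435 - 330 = 105 |
| Week 60 to 72 (same for all later pairs) | 407-435; 491-519 | 491 - 435 = 56 | 84 | 519 - 407 = 112 |

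With once-daily dosing, 84 days is 84 doses. For contrast, RAJ1 subjects on 4-week visits wait 14-42 days (Week 4 to 8: 50 - 36 = 14; 64 - 22 = 42).

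**First possible stop.** Section 7 states: "For the evaluation of safety, Week 0 of this extension study (015K-CL-RAJ2) will be referred to as the baseline". Week 0 cannot exceed 150% of itself, so for an RAJ3/RAJ4 subject the first qualifying pair is Weeks 12 and 24. The rule cannot be met before the Week 24 visit (Day 162 to 176).

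**A first high value from an unscheduled sample.** Two Scheduled Visits are still needed. If the sample is drawn the day after an earliest Week 60 visit (Day 408), the Week 84 visit may be as late as Day 603: 603 - 408 = 195 days.

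**Share on 12-week visits throughout.** The documents give no exact figure. Taking the RAJ1 entrants from the planned total gives (800 - 201)/800 = 599/800 = 75%. Using the components in Section 7.1 gives (300 + 510)/(201 + 300 + 510) = 810/1011 = 80%. Both are approximations, and the delay does not depend on them.

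**Where the item 1 limits sit on the SAP Appendix 9 scale.**
- Hemoglobin, lymphocytes and platelets: Grade 3.
- ANC and CPK: Grade 4.
- Creatinine: the top of Grade 1, which ends at 1.5 x the Week 0 value; Grade 3 begins above 3.0 x the Week 0 value.

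**The case against.** The strongest objection is that the protocol has no rule that a Grade 3 value triggers a numeric stop. ANC and CPK stop only at Grade 4. Liver tests have no mandatory numeric stop: even ALT or AST above 3 x ULN with bilirubin above 2 x ULN leads only to considering discontinuation (Appendix 6). Creatinine acts from a lower grade and asks for persistence in exchange. This stands. A reader might infer that creatinine is held to a laxer standard than the protocol sets for itself; the documents do not support that.

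A second objection is that several routes allow earlier action:
- investigator judgement or sponsor request (3.4.1.1, items 5 and 6), where item 5 is in the same act-without-delay list;
- discontinuation criteria 7 and 12 (Section 3.4);
- adverse event recording and follow-up (5.5.1, 5.5.6), with acute renal failure always reported as serious (Appendix 3);
- DSMB review, including individual subjects' data and urgent review (2.2.2, 10.1);
- in Korea and Taiwan, dose reduction for an adverse event of Grade 2 or higher (5.1.2).

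This also stands. It would be wrong to infer that dosing must continue for 56-112 days: the figure is the wait for the numeric stop, not expected exposure. However, none of these routes sets a creatinine value. The contacts between visits (5.1.4) may reveal symptoms but do not measure creatinine.

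Third, the clinical weight is limited. Section 1.3 reports changes in creatinine level and names no kidney event, and Section 1.4 does not list the kidney among the primary areas of toxicity. A reader might infer an established renal risk; the documents do not show one.

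**Conclusion.** The point holds as a modest one. On 12-week visits, the only numeric creatinine stop waits for the next Scheduled Visit, nominally 84 days, whatever the size of the first value, and an early confirmatory sample cannot bring it forward. The case for change is that a very high single value needs no persistence filter and the SAP already defines the level. The two-visit rule at 150% is itself defensible.

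The figures rest on four assumptions:
- The baseline in Section 3.4.1.1 is Week 0. That section does not say so, but the key-terms definition (last value before dosing) and Section 7 both point there.
- The analysis windows describe actual visit spacing. Visit dates apply in principle (Table 1, note u), so 112 days is not a hard limit.
- The next Scheduled Visit value is also above 150%; otherwise no numeric stop occurs.
- No one acts earlier through the discretionary routes.

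The documents give no frequency of creatinine above 150% or above 3.0 x baseline, so the number of affected subjects cannot be estimated.

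**What to change.** Amend Section 3.4.1.1 and the Synopsis as follows.
1. Add a single serum creatinine above 3.0 x baseline as a suspension criterion. Allow resumption only once a retest is at or below 150% of baseline or, if it lies between 1.5 and 3.0 x, on a documented investigator risk/benefit decision. Without this clause, a fall from 3.1 to 2.9 x would clear the new criterion under the general resumption rule in Section 3.4.1.
2. Require an unscheduled creatinine retest within about 1 week of any value above 150% of baseline, with the investigator deciding on suspension from the result.
3. Keep the two-visit rule as the mandatory stop for 1.5 to 3.0 x baseline.

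Naming Week 0 as the baseline in the same sentence would remove the remaining ambiguity.

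The cost is a few sentences, plus an unscheduled visit and a central-laboratory sample for each affected subject. The visit schedule does not change. A few more suspensions are possible. Any longer than 7 days becomes an interruption under Section 3.4.1: at most 4 consecutive weeks, twice a year, at least 16 weeks apart, with withdrawal beyond that. Because continued access to active drug is a study objective (Section 2.1), the retest at 150% should inform the investigator and not force a stop.
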